Neurofeedback Enhanced Cognitive Reappraisal Training

Principal Investigator (PI): [name] [name]

University of Michigan

Dept of Psychiatry

[name]

Email: [contact]

Co-Investigator(s):

[name], [name], [name], [name], [name], [name], [name]

Sponsor:

Brain & Behavior Research Foundation

HUM Number:

HUM00209563

NCT Number:

NCT06132659

Version:

3.21.2025

DETAILED IRB PROTOCOL**1. Objective**

Anxiety disorders are the most common mental health condition worldwide and a leading cause of disability. The development of novel interventions to treat anxiety has lagged the advancements made regarding the neurobiology of emotion and cognitive processes directly related to treatment. This proposal will utilize real-time functional magnetic resonance imaging neurofeedback (NF) to modulate key brain regions involved in emotion regulation to enhance effectiveness of cognitive reappraisal, a central skill taught in evidenced-based psychotherapies. This innovative project will identify 1) the ability of adults with anxiety to self-modulate brain function in regions specific to healthy emotion regulation using NF and 2) the potential impact of neuromodulation on improved emotion regulation ability and anxiety reduction.

2. Specific Aims/Hypotheses

Aim 1A. Evaluate the ability of adults with anxiety to increase prefrontal cortex activity during CR based on NF.

Primary outcome 1A: BOLD activation. Change in PFC activity (baseline to transfer run) from the reappraise > look contrast.

Hypothesis 1A: Participants receiving veritable-NF will show a greater activation increase in the PFC compared to sham-NF.

Aim 1B. Determine the relationship between prefrontal cortex activity recruitment and CR ability in adults with anxiety.

Primary outcome 1B: Negative affect ratings. Decrease in negative affect ratings (baseline to transfer run) from reappraise > look contrast.

Secondary outcome 1B: Prefrontal-amamygdala connectivity. Change in amygdala-PFC functional connectivity (baseline to transfer) from reappraise > look contrast.

Hypothesis 1B1: Participants receiving veritable-NF will show greater CR ability compared to those receiving sham-NF.

Hypothesis 1B2: prefrontal cortex activation will positively correlate with CR ability.

Aim 1C. Assess the impact of NF on anxiety symptoms and CR use over time (exploratory).

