4.3.2 Study Visit 1: Informed Consent, Diagnostic Interview

Informed Consent. The informed consent form will be mailed in advance of the visit. During this first study visit, participants will be given detailed information about the study. During this meeting, the potential subject will be encouraged to ask questions about the study, after which the informed consent form will be reviewed and signed. Study staff will go through and explain the informed consent document to the participant, which will be available and visible on SignNow. After the participant digitally signs the document, the research assistant will sign the document.

Diagnostic Interview and Questionnaires. Consented participants will then undergo a diagnostic interview, including the clinician-administered SCID-5 and CGI (see Section 4.5.1). This diagnostic assessment will be used to make the final determination about study eligibility. Participants will also be given the HAM-A to assess baseline anxiety severity in the past week. This visit may take 1-3 hours in total, depending on how many symptoms a subject endorses.

Randomization. Participants who meet eligibility criteria following the diagnostic interview will be invited to schedule Study Visits 2 and 3. Study Visit 2 will occur 1-5 days before Study Visit 3. In arms 2 and 3, a designated member of the study staff who will remain *unblinded* during the duration of the study will randomly assign participants to one of the two groups (veritable-NF or sham-NF). Approximately one-half of the sample will be assigned to each group. All staff interacting with the participant, including the participant themselves, will be *blinded* to group assignment. To this end, the unblinded staff member will code the MRI scanning sequences with sets of random numbers that will be used to communicate to the MRI Technician which neurofeedback protocol should be employed during each study visit without revealing visually or by name if true feedback is being generated.

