Emotion Regulation Task. Half the participants will be randomized to complete the ERT with veritable feedback from the PFC as described in Phase 2. The specific region of interest (dmPFC or vLPFC) will be determined by the results of Phase 2 and arm 1 of Phases 3 and 4. Participants in the sham group will complete the same ERT as the veritable nf-group, however, the thermometer will display a pseudo-random feedback signal. This signal is generated to match the spectral characteristics of true feedback (established from Phase 2), including the same average success rate to control for the rewarding aspects of receiving feedback. As participants are blind to group assignment, inclusion of a sham-group controls for practice effects, fatigue, and learning that may occur without NF. On each trial of the task, a 4s presentation of vLPFC/dmPFC activity (reappraisal trials) or a crosshair (look trials) will appear following the image presentation screen. In the first functional run ('baseline'), participants complete the ERT without NF to establish baseline activity in the two regions of interest (ROIs: vLPFC and dmPFC), based on masks from previous CR meta-analyses (e.g., ^{20,21}). In the middle runs, participants complete the ERT with NF. In the final functional run ('transfer'), participants again complete the ERT without NF to establish ability to implement learning from NF training.

The NF set-up will utilize custom software, developed by co-investigator [name]. This includes motion correction, linear trend removal and spatial smoothing for each image presentation. The BOLD percentage signal change within the ROI is calculated using most recent "reappraise > look" contrast and fed back as a visual display reflecting BOLD signal change. The feedback display shows a thermometer whose minimum is initially set at 0% signal change. Bars fill the thermometer image to correspond to the increase in participant's brain activity using custom MATLAB scripts. On no feedback runs (baseline and transfer), the display shows a crosshair or a static thermometer.

Post-NF interview.

- Difficulty to complete the task
- Comments and suggestions about the task, including appraisals, affect, and arousal ratings of the images
- Perceived control of brain activity and perceived success of CR during NF³⁵
- Tolerability and acceptability of NF
- Manipulation check of group assignment

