4.6 Compensation

It is important that participants feel adequately compensated for the time spent participating in the various components of the study, including completing the diagnostic interview, being scanned, performing the NF task, completing self-report measures, and traveling to the research site.

	Amount
Baseline Assessment:	\$20
Training:	\$20
MRI Scan:	\$50
Follow-Up Assessments:	\$20

Participants who complete the study will be eligible to receive up to \$110.

These values are similar to those used by other fMRI studies at the University of Michigan. If participants withdraw from the study early, they will be paid for the parts of the study they completed. Participants will be paid by check or gift card.

If a participant is asked to return for a second MRI scan brought on by scanner or neurofeedback malfunction, they will be compensated accordingly.

5. Participant Withdrawal

Participants may withdraw from the study at any time for any reason. The reasons a participant may withdraw include, but are not limited to:

- feeling claustrophobic in the MR scanner
- not desiring to continue

Researchers may withdraw a participant from the study if they have a reason to doubt the quality or validity of the data the participant would provide. Reasons may include, but are not limited to:

- participant being unable to hold still in the scanner
- participant no longer meeting criteria
- participant being unable to perform required tasks
- participant not complying with researcher or MRI tech instructions

6. Statistical Design

Aim 1. Evaluate the ability of adults with anxiety to increase prefrontal cortex activity during CR based on NF.

The task will be processed and analyzed using the same methods as Aims 1 and 2. To assess group differences in neuromodulation ability (**hypothesis 1**), a repeated-measures linear mixed effects model (LME) with participant as a random intercept, will examine the 3-way interaction of group (veritable-NF, sham-NF) x condition (reappraise, look) x time (baseline, NF1, NF2, NF3, transfer) on extracted BOLD activation from the dm/vLPFC mask.

Aim 1B. Determine the relationship between prefrontal cortex activity recruitment and CR ability in adults with anxiety.

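### The Aim 1A model treats the pre-feedback baseline run as a free outcome level instead of adjusting for it, so the arm effect at transfer is a raw change difference estimated less precisely than the data allow

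*Combined protocol and SAP*

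**What the plan says.** Section 2 (Specific Aims/Hypotheses) defines primary outcome 1A as "Change in PFC activity (baseline to transfer run) from the reappraise > look contrast". The hypothesis is directional between arms: "Participants receiving veritable-NF will show a greater activation increase in the PFC compared to sham-NF".

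Section 4.5.2, under Emotion Regulation Task, describes the runs. "In the first functional run ('baseline'), participants complete the ERT without NF to establish baseline activity"; feedback is given in the middle runs; and "In the final functional run ('transfer'), participants again complete the ERT without NF".

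Section 6, Aim 1, analyses the extracted activation with "a repeated-measures linear mixed effects model (LME) with participant as a random intercept", which "will examine the 3-way interaction of group (veritable-NF, sham-NF) x condition (reappraise, look) x time (baseline, NF1, NF2, NF3, transfer"). Baseline is therefore one of five levels of time. For Aim 1A no baseline covariate is named and the arms are not constrained to a common baseline mean. Section 6 uses the same form, with baseline as a time level, for affect ratings, HAM-A and ERQ.

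On allocation, Section 4.3.2 says "Approximately one-half of the sample will be assigned to each group". No sample size, power, SD, significance level or run-to-run correlation is given for Aim 1A.

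**The concern.** The baseline run precedes all feedback. It comes after assignment, but participants and the staff who deal with them are blinded, so it can serve as a pre-treatment covariate. The plan instead lets each arm have its own baseline mean and subtracts the baseline contrast in full. Full subtraction is optimal only if the contrast correlates perfectly between runs. A difference between two BOLD estimates from a single run is likely to be noisy, and all of that noise enters the arm comparison.

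The random intercept does not repair this. It is common to a participant's reappraise and look values, so it drops out of their difference. H1A is the lead hypothesis and normally rests on one scan session per participant. Avoidable imprecision makes a real neurofeedback effect easier to miss.

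**Working it through.** The plan states no figure for Aim 1A that could be reproduced, so the check is algebraic, supported by simulation.

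**Inputs.** From the documents: the outcome (transfer minus baseline, reappraise minus look), five runs, two conditions, a participant random intercept only, and roughly 1:1 allocation. Assumed: equal variance s² of the contrast at baseline and transfer; correlation rho from 0 to 0.7; two-sided 5% test; 80% power as an anchor; 30 per arm in simulations.

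**Step 1: what the coefficient is.** With free group x condition x time means and complete runs, the transfer-versus-baseline three-way coefficient equals the arm difference in mean change of the contrast. Fitting the planned model to two simulated data sets gave 0.8101 against 0.8101 (rho = 0) and 0.3044 against 0.3044 (rho = 0.5).

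**Step 2: variance per participant.**
- Change score: 2(1 − rho)s².
- Baseline-adjusted: (1 − rho²)s².
- Ratio: 2(1 − rho)/[(1 − rho)(1 + rho)] = 2/(1 + rho).

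**Step 3: power.** An effect detected with 80% power lies 1.960 + 0.842 = 2.802 standard errors from zero. Adjustment multiplies this by √[2/(1 + rho)]. At rho = 0.5, for example, 2.802 × 1.155 = 3.235, and 3.235 − 1.960 = 1.275, giving 89.9%.

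| rho | Variance, change / adjusted | Power, change score | Power, ANCOVA |
|---|---|---|---|
| 0 | 2.00 | 80% | 97.7% |
| 0.3 | 1.54 | 80% | 93.5% |
| 0.5 | 1.33 | 80% | 89.9% |
| 0.7 | 1.18 | 80% | 86.0% |

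Simulated variance ratios (6,000 trials per rho) were 2.00, 1.49, 1.35 and 1.17. Both estimators were unbiased, with means of 0.49 to 0.50 for a true effect of 0.50. The table compares a correctly computed change-score test with ANCOVA. It does not describe the planned mixed model.

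**Step 4: the planned model's own standard error.** Suppose rho arises from a stable person-level contrast b with variance rho·s², with residuals otherwise independent.
- Each participant supplies 5 × 2 = 10 values, with 9 within-person degrees of freedom.
- b shifts each value by ±b/2. This adds 10 × (b/2)² = 2.5b² to the within-person sum of squares, so the estimated residual variance is about (1 − rho)s²/2 + 2.5·rho·s²/9.
- The change in the contrast combines four values, so the model assigns it 4 times that residual variance.

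At rho = 0.5 the model's figure is 4 × (0.250 + 0.139) = 1.556 (in units of s²), against a true 2(1 − 0.5) = 1.0. The standard error is too large by √1.556 = 1.247, so the effective critical value is 1.960 × 1.247 = 2.445. Type I error is then about 1.4%. Power for the effect in Step 3 is P(Z > 2.445 − 2.802 = −0.357), about 64%. Simulation of the five-run model with 30 per arm agrees: 64% power and 1.3% type I error, with ANCOVA at 88%.

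**The case against.** The strongest defence is that the model matches the stated outcome. Outcome 1A is a change, the interaction estimates change, and the estimate is unbiased. That stands: this is a choice that costs precision, not an error or a contradiction.

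The size is also unknown, because the documents supply none of the quantities needed. A reader might infer that the planned analysis has twice the necessary variance. The documents do not support that as a statement about this trial. Two is the value at rho = 0. The random-intercept model does imply rho = 0 for the contrast, but a one-line model statement is not a claim that reappraisal activity is uncorrelated across runs in one session. Section 3 describes reduced prefrontal recruitment during reappraisal as characteristic of anxious patients, and H1C2 treats PFC change as an individual-difference predictor. Both sit poorly with zero correlation. At rho = 0.7 the excess variance is 18%.

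A reader might also take the ANCOVA figures as the gain over the planned test. They are not. The plan names the five-run interaction, a 4-df test ((2 − 1) × (2 − 1) × (5 − 1)), and no transfer contrast. For rho above 0, much of the planned model's shortfall comes from its covariance structure and the omnibus test, not from the missing adjustment. At rho = 0.5, for an effect that a change-score test detects with about 80% power, simulation with 30 per arm put the omnibus test at about 55%.

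Finally, adjusting a single transfer contrast changes the primary test as well as adding a covariate. That is correct and belongs in the cost.

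**Conclusion.** The point holds as a conditional recommendation on precision. The arm effect that answers outcome 1A is a raw change difference, exactly so with complete runs and approximately with missing ones. Its variance exceeds that of a baseline-adjusted comparison by a factor of 2/(1 + rho), which is above 1 for any rho below 1. Over rho = 0 to 0.7 the excess runs from 100% down to 18%. Where in that range this trial lies cannot be determined from the documents.

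If rho is above 0, the random-intercept-only structure adds a separate loss by overstating the standard error. The figures of about 64% power and 1% type I error at rho = 0.5 rest on the residual structure in Step 4.

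Bias or an inflated false-positive rate should not be inferred. Both estimators are unbiased under randomisation, and the planned test errs towards too few rejections. The change is worth making before analysis because the baseline data are already collected and the question stays the same.

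**What to change.** In Section 6, Aim 1, name the arm difference at the transfer run as the H1A test. Estimate it by regressing the transfer-run reappraise-minus-look PFC contrast on arm and the participant's baseline-run contrast, and report the adjusted difference with its 95% CI. With baseline in the model, the arm coefficient is the same whether the outcome is written as transfer or as change, so the endpoint in Section 2 is unaffected.

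An alternative is to keep all five runs in a model for the contrast, with a common baseline mean across arms and a run covariance that allows stable person differences in the contrast. That covariance can be unstructured if the sample size permits. Otherwise, use a participant random slope for condition.

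In either case, keep the five-run group x condition x time model as a supporting analysis of the neurofeedback runs.

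**Cost.** The covariate takes one degree of freedom. H1A becomes a single pre-specified transfer contrast in place of the 4-df omnibus interaction, so NF1 to NF3 no longer contribute to the primary test. That is a real change to the plan, but it brings the test into line with the stated outcome. No new data, visits or participants are needed.

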To assess group differences in CR ability (**hypothesis 1B1**), a repeated-measures LME with participant as a random intercept, will examine the interaction of group (veritable-NF, sham-NF) x condition time (baseline, NF1, NF2, NF3, transfer) on negative affect ratings and prefrontal-amamygdala connectivity during the ERT. We will use a psychophysiological interaction analysis to measure prefrontal-amamygdala connectivity. Deconvolved time series from anatomical bilateral amygdala seeds for each participant will be multiplied by a vector for the reappraise > look contrast at each run. Regressors for the seed time series, the original condition and the interaction term will be convolved with the canonical hemodynamic response function. Contrast maps will be entered into second-level random effects analyses to test if veritable-NF shows greater prefrontal-amamygdala connectivity than sham-NF.

For hypothesis 1B2, linear regressions will examine run-by-run associations between dm/vlPFC activity and 1) negative affect ratings and 2) prefrontal-amamygdala connectivity, across all participants irrespective of training condition.

Aim 1C. Assess the impact of NF on anxiety symptoms and CR use over time (exploratory).

To examine the effect of NF on anxiety (**hypothesis 1C1**), a repeated-measures LME with participant as a random intercept, will examine the effect of time (baseline, 1 month) x group (veritable-NF, sham-NF) on the HAM-A. To examine the effect of NF on CR use (**hypothesis 1C1**), a repeated-measures LME with participant as a random intercept will examine the interaction of time (baseline, 2-week, 1-month) x group (veritable-NF, sham-NF) on the ERQ.

Linear regressions will examine the association between dm/vlPFC change (transfer-baseline) and change in HAM-A and ERQ scores (1 month – baseline) across all participants (**hypothesis 1C2**). Exploratory: Mediation will test if change in dm/vlPFC activity mediates the relationship between NF group and change in HAM-A or ERQ scores.

7. Data and Safety Monitoring Plan

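### The secondary connectivity outcome is a baseline-to-transfer change, but neither planned connectivity analysis names that contrast, and the model's condition term does not fit the PPI as written

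*Combined protocol and SAP*

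**What the plan says.** Section 2, Aim 1B, defines the secondary outcome as "Change in amygdala-PFC functional connectivity (baseline to transfer) from reappraise > look contrast". The linked hypothesis, 1B1, is more general: "Participants receiving veritable-NF will show greater CR ability compared to those receiving sham-NF". It mentions neither connectivity nor change.

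Section 6, Aim 1B, then describes two analyses of connectivity.

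- **A repeated-measures mixed model** with a random participant intercept. It tests group "x condition time (baseline, NF1, NF2, NF3, transfer) on negative affect ratings and prefrontal-amamygdala connectivity during the ERT". One sentence covers both the affect ratings and connectivity.
- **A second-level analysis of PPI contrast maps**: "Contrast maps will be entered into second-level random effects analyses to test if veritable-NF shows greater prefrontal-amamygdala connectivity than sham-NF".

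The PPI itself is built from amygdala seed time series that "will be multiplied by a vector for the reappraise > look contrast at each run".

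Two neighbouring passages show that the plan can be more exact. The Aim 1 model in Section 6 gives condition its levels and places it in a "3-way interaction of group (veritable-NF, sham-NF) x condition (reappraise, look) x time (baseline, NF1, NF2, NF3, transfer"). For Aim 1C the plan names a difference between two runs: "Linear regressions will examine the association between dm/vlPFC change (transfer-baseline) and change in HAM-A and ERQ scores".

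**The concern.** The outcome compares two particular runs, transfer and baseline. The second-level sentence asks only whether one arm has greater connectivity than the other. An analyst could follow it with maps averaged over runs, with transfer maps alone, or with transfer-minus-baseline maps. The mixed model covers all five runs, but its interaction asks whether the arms' profiles differ anywhere, not whether they differ from baseline to transfer.

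The condition term adds a second problem. If each run yields one reappraise > look coefficient, condition has already been contrasted out and no condition factor is left to enter for connectivity.

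At stake is the meaning of the reported connectivity result. Several defensible analyses could be run, they can disagree, and the choice could be made after the results are seen. The transfer run is there to show whether learning carries over once feedback stops, so a result driven by the feedback runs would answer a different question.

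**Working it through.** The documents give no sample size, SD, correlation, effect size or alpha for this test, so there is no planned figure to reproduce. The check is structural first, then illustrative.

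**1. Does the mixed model contain the stated outcome?** Order the runs as baseline, NF1, NF2, NF3, transfer. Transfer minus baseline has weights c = (−1, 0, 0, 0, 1). These sum to zero, so c lies inside the 4-df group x time interaction. The model can estimate the outcome as a single 1-df contrast.

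**2. Is the interaction test specific to that contrast?** No. Assume 30 per arm, SD 1, run-to-run correlation r = 0.5, two-sided alpha 0.05, and an arm difference of 0.8 SD in the three NF runs but none at baseline or transfer.

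- Mean difference over runs: 3 × 0.8 / 5 = 0.48.
- Sum of squared deviations: 2 × 0.48² + 3 × 0.32² = 0.768.
- Noncentrality: (30/2) × 0.768 / (1 − 0.5) = 23.04, on 4 and 58 × 4 = 232 df.
- Power: 98%, although baseline-to-transfer change does not differ between arms.

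**3. What does a run-averaged arm comparison test?** Its weights are (1/5, …, 1/5), and their product with c is (−1 + 1)/5 = 0. It carries no information specific to the change. With a true constant arm offset of 0.5 SD and no change (30 per arm), it rejects 82%, 69% or 59% of the time at r = 0.3, 0.5 or 0.7, while the change test stays at 5%. This shows that the two tests answer different questions. It is not a false-positive rate, because randomisation makes the expected baseline offset zero.

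**4. What does a transfer-only comparison cost?** Under randomisation it has the same expected arm difference as the change; only precision differs. With unit variance per run, the variances are 1 for transfer-only, 1 − r² for baseline-adjusted and 2(1 − r) for the change score. Power = P(Z > 1.96 − 2.80 × s), where s is the standardised signal relative to a benchmark with 80% power. For transfer-only, s = √(1 − r²) against the baseline-adjusted test and √(2(1 − r)) against the change score.

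| r | s, adjusted benchmark | power | s, change benchmark | power |
|---|---|---|---|---|
| 0.3 | 0.954 | 76% | 1.183 | 91% |
| 0.5 | 0.866 | 68% | 1.000 | 80% |
| 0.7 | 0.714 | 52% | 0.775 | 58% |

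**5. What does averaging all five runs cost?** The variance of the five-run mean is (1 + 4r)/5. The mean effect is 0.5 of the transfer effect for a steady build-up (0, 0.25, 0.5, 0.75, 1) and 0.8 if the full effect is present from NF1. So s is the mean effect times the benchmark SD, divided by √((1 + 4r)/5). For example, steady build-up at r = 0.5 against the adjusted benchmark gives 0.5 × 0.866 / 0.775 = 0.559, hence 35%.

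| r | steady, adjusted benchmark | steady, change benchmark | full from NF1, adjusted benchmark |
|---|---|---|---|
| 0.3 | 52% | 70% | 90% |
| 0.5 | 35% | 44% | 71% |
| 0.7 | 21% | 24% | 45% |

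Averaging can gain or lose power, depending on the build-up and the correlation.

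**6. Does condition fit?** The PPI regressor is the seed "multiplied by a vector for the reappraise > look contrast at each run", which gives one estimate per run. A reappraise/look factor needs two. In the Aim 1B model, condition has no levels and no multiplication sign before time, unlike in the Aim 1 model.

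**The case against.** A reader might infer that the secondary outcome is not tested at all. The documents do not support that: the mixed model is applied to connectivity, its time factor includes baseline and transfer, and step 1 shows that it contains the contrast. This part of the defence stands. It does not supply the missing statement of which contrast decides.

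A reader might also infer that the second-level test must either average in the baseline run or ignore it. The sentence closes a paragraph that opens with the five-run model and builds the PPI run by run, so transfer-minus-baseline maps fit its wording too. It is under-specified, not committed to a poor choice.

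Nor can one say that a PPI never admits a condition factor. Separate condition regressors would give condition-specific estimates; the mismatch is with the single-vector PPI described. The phrase may contain a leftover word or have lost a multiplication sign, possibly when the PDF was read. Condition could also have been meant for the affect ratings, which share the sentence and whose outcome is a reappraise > look contrast.

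Finally, a loss of precision is not general. Against a change score, which is the outcome as defined, transfer-only testing is more powerful at r = 0.3 and equal at r = 0.5. Preferring baseline adjustment to a change contrast is an efficiency choice, not the correction of an error.

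**Conclusion.** The concern holds in a limited form. The stated secondary outcome is not specifically tested: there are two non-equivalent connectivity analyses, neither names the arm difference in transfer versus baseline, and no rule says which one decides. Separately, condition does not fit the PPI as written and has to be reconciled with it.

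These conclusions rest on the text alone. The power figures do not come from the plan. They assume equal variances, equal correlation between all runs, two-sided alpha 0.05 and, in steps 2 and 3, 30 per arm. They show that the choice of analysis can matter, in a direction and to a degree that depend on the correlation, the benchmark and how the effect builds up. This affects one secondary outcome. It should be corrected, but it does not undermine the trial.

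**What to change.** In Section 6, Aim 1B:

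1. State that connectivity enters as one PPI estimate per participant per run (reappraise > look).
2. Remove condition from the connectivity model, and write the affect-rating model in a separate sentence with its own factors and levels.
3. Name one 1-df test as the test of the secondary outcome: either the arm difference at transfer with the participant's baseline estimate as covariate, or the group x (transfer − baseline) contrast within the mixed model. Label the 4-df interaction as supportive.
4. If the second-level analysis is kept, enter transfer-minus-baseline maps, or transfer maps with baseline as covariate, and say that it is supportive.

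The cost is wording. The baseline and transfer runs are already part of the scan, so no new data are needed. The change should be made before anyone sees connectivity results by arm.

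### Hypothesis 1B2 is tested run by run over five runs with no deciding result, significance level or participant term, so the plan does not secure its error rate

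*Combined protocol and SAP*

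**What the plan says.** Section 2 states Hypothesis 1B2 as one claim: "prefrontal cortex activation will positively correlate with CR ability". It serves Aim 1B, whose purpose is given as "Determine the relationship between prefrontal cortex activity recruitment and CR ability in adults with anxiety". Aim 1C is labelled exploratory; Aim 1B is not.

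The analysis in Section 6 is one sentence: "linear regressions will examine run-by-run associations between dm/vlPFC activity and 1) negative affect ratings", with prefrontal-amygdala connectivity as the second outcome. Both arms are pooled. The sentence gives no number of runs. The count of five comes from the time factor of the neighbouring models, for example "time (baseline, NF1, NF2, NF3, transfer) on extracted BOLD activation".

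Three other texts bear on how to read it:

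- Section 2 defines the Aim 1 outcomes as one change per person. For the brain measure this is "Change in PFC activity (baseline to transfer run) from the reappraise > look contrast". Negative affect is defined in the same way and ranked primary; connectivity is ranked secondary.
- For Hypothesis 1C2, Section 6 uses the same term with one row per person: "Linear regressions will examine the association between dm/vlPFC change (transfer-baseline) and change in HAM-A and ERQ scores".
- For Hypothesis 1B1, Section 6 specifies "a repeated-measures LME with participant as a random intercept, will examine the interaction of group" by time. The models for Hypotheses 1 and 1C1 also carry a participant random intercept. The 1B2 sentence does not.

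**The concern.** One hypothesis is given five results per outcome, and nothing fixes which of them answers it. The outcome definitions in Section 2 do not help, because they name a change and the 1B2 analysis does not use it.

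Two models fit the wording. The more natural one is a separate regression per run, since the same section uses the term that way for 1C2. No participant term is then needed, but there are five tests. The other is a single regression on all runs stacked, in which a person's five rows are treated as independent.

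The stake is the brain-behaviour link. Hypothesis 1B2 is the only planned test of that link during the task; 1C2 and the mediation analysis use change in HAM-A and ERQ at follow-up. With the rule open, one favourable run out of five could be reported as confirmation. In a stacked model, chance alignment of stable differences between people could be.

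**Working it through.** The documents give no sample size, significance level or error rate for 1B2, so there is no planned figure to reproduce. The checks below assume no true association, two-sided 0.05 per test and one prefrontal measure.

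**Inputs.** Five runs, from the time factor in Section 6. Two outcomes, from the 1B2 sentence. Assumed, because the documents give neither: N from 30 to 100, and ICCs from 0 to 0.7, equal in both variables.

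**Reading 1: one regression per run.**

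- Each test alone: about 5% (simulated 4.9 to 5.1%).
- At least one of five significant, independent runs: 1 − 0.95^5 = 22.6%. With correlated runs, simulation (20,000 replicates per case) gives about 18 to 23%.
- At least one of five in the predicted direction: 1 − 0.975^5 = 11.9%; simulated about 9 to 12%.
- At least one of five at 0.01: 1 − 0.99^5 = 4.9%; simulated about 4 to 5%.
- Counting both outcomes equally gives ten tests: 1 − 0.95^10 = 40.1% if independent. Section 2 ranks affect above connectivity, so the per-outcome figure is the fairer one.

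**Reading 2: runs stacked, no participant term.** The design effect is DE = 1 + (5 − 1) × ICC_x × ICC_y, and the actual error is 2[1 − Φ(1.96/√DE)].

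| ICC (both variables) | DE | Error |
|---|---|---|
| 0 | 1.00 | 5.0% |
| 0.2 | 1.16 | 6.9% |
| 0.3 | 1.36 | 9.3% |
| 0.5 | 2.00 | 16.6% |
| 0.7 | 2.96 | 25.5% |

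Simulation agrees closely and hardly depends on N. If either ICC is 0, DE = 1 and the error stays at 5%.

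**Does the mixed-model remedy hold its level?** For the within-person coefficient with model-based errors, simulated error is 4.8 to 5.3% with a common slope and exchangeable errors. It rises to 7.3 to 7.8% with AR(1) errors at 0.5, and to 9.5 to 9.9% or 15.7 to 16.4% if person slopes vary (SD 0.3 or 0.5). With leave-one-participant-out clustered errors it is 4.4 to 5.6% in all these cases.

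**Precision.** With equal ICCs, interval widths are proportional to:

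- per-run regression: 1/√N
- nominal stacked regression: 1/√(5N)
- within-person coefficient: 1/√(4N)
- between-person coefficient: 1/√N
- change-on-change regression: 1/√N

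The within-person interval is therefore 1/√4 = 0.50 times a per-run interval, and the between-person and change-score intervals are about equal to it. Against the nominal stacked interval, the within- and between-person ratios are √(5/4) = 1.12 and √5 = 2.24.

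With leave-one-participant-out errors, the within-person interval relative to the stacked one is 1.13 to 1.19 (common slope), 1.26 to 1.31 (AR(1) 0.5) and 1.37 to 1.72 (varying slopes). Divided by √5, these are 0.51 to 0.53, 0.56 to 0.59 and 0.61 to 0.77 of a per-run interval.

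**The case against.** The strongest reply is that the plan is silent rather than wrong. On the natural reading every regression is valid at its own level, and no participant term is missing. A reader might infer that 1B2 carries a false-positive rate above 20%. The documents do not support that: the figure needs a rule under which any significant run counts, and the plan contains no such rule.

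A reader might likewise infer that clustering has been ignored. That holds only on the less natural stacked reading, and its size rests on assumed ICCs. Section 2 defines the measures by a reappraise-minus-look contrast, and connectivity is built that way ("multiplied by a vector for the reappraise > look contrast at each run"). Such a contrast removes a person's overall level, so ICCs may be low and stacked error near 5%. The 1B2 sentence itself names no contrast for activity or ratings, however, so this protection is possible but not specified.

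It is also fair that 1B2 is a pooled, correlational hypothesis and that a short clarification could settle it. Both points stand, and they limit the weight of the concern. They do not supply the missing rule.

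**Conclusion.** The plan does not secure the error rate for 1B2, because neither the deciding result nor the level is fixed and the model can be read in two ways. Confidence in that is high, since it is read directly from Section 6. Confidence in any particular inflation is low: the per-run range depends on an any-run rule, the stacked range depends on assumed ICCs, and an error near 5% cannot be excluded on either reading.

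It would be wrong to carry this over to the trial's main comparisons. Hypotheses 1A and 1B1 compare randomised groups with models that include a participant effect, and they are not affected. The point should be settled before outcome data are analysed.

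**What to change.** **Preferred.** In Section 6, replace the run-by-run regressions with one mixed model per outcome over all five runs. Include a participant random intercept, a run term, and prefrontal activity split into within-person and person-mean parts. Name the within-person coefficient as the single test of 1B2, with leave-one-participant-out clustered standard errors, and report the between-person coefficient descriptively. Negative affect decides and connectivity is secondary, as Section 2 already ranks them.

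**Equally acceptable and simpler.** Regress baseline-to-transfer change in affect on baseline-to-transfer change in prefrontal activity: one row per person and one test. This uses the outcomes in Section 2 and the form already used for 1C2. Label the per-run results descriptive.

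**If per-run regressions stay as the test.** Name one deciding run, or test the five affect regressions at 0.05/5 = 0.01 each.

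**To reconcile first.** Use a reappraise-minus-look affect contrast only if ratings are collected by condition in each run. Section 4.5.2 describes a rating at the end of the run for Phase 1 and gives no rating schedule for the randomised task. Section 2 presupposes ratings by condition. These texts must be brought into line.

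**Cost.** A short paragraph and slightly more analysis. Compared with a single per-run regression, the within-person interval is about half as wide under a common slope and exchangeable errors, with less gain otherwise; the between-person interval is about the same. Only against the nominal stacked interval, which is not valid when runs are correlated within people, are they wider (about 1.1 and 2.2 times). The change-score option gives up the within-person gain in precision.
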